3.1.2 Event Data

Analyses of the clinical endpoints will use the CEC-adjudicated data for death, MI, stroke, coronary revascularization, or hospitalization for unstable angina.

3.1.3 Assessment of Model Assumptions

The validity of the proportional hazards assumption will be examined using a standard graphical method such as Schoenfeld residual plots. If the assumption holds, the survival curves should be approximately parallel to each other. An additional analytical method that includes the supremum test as implemented by using the ASSESS statement in PROC PHREG in SAS version 9.4 may be utilized. A *P*-value of < 0.05 indicates violation of the proportional hazards assumption. If there is evidence of non-proportionality, a time dependent covariate will be included in the model, or a restricted mean survival time model will be performed.

3.1.4 Multiple Comparisons and Composite Endpoints

With the number of primary hypotheses and the various secondary endpoints to be analyzed and compared, there is an increased probability that at least one of the comparisons could be "significant" by chance. We have pre-specified the primary and secondary outcome variables to help avoid over-interpretation and to reduce the problems inherent with multiple testing. We will be conservative in the interpretation of these analyses, taking into account the degree of significance, and looking for consistency across endpoints.

3.2 Primary Endpoint Analysis

The primary endpoint is the composite of all-cause mortality, MI, stroke, coronary revascularization, or hospitalization for unstable angina.

If two of the component events of the primary composite endpoint occur on the same day, the following hierarchy will be used when reporting the components of the primary endpoint. For example, a patient with stroke and all-cause mortality on the same date will be considered as having stroke when summarizing individual events within the primary composite outcome. This hierarchy will only be used for summarizing events within the primary composite outcome and will not affect the primary analysis.

- i. MI
- ii. Stroke
- iii. Hospitalization for unstable angina
- iv. Coronary revascularization
- v. All-cause mortality

3.2.1 Primary Analysis

The primary objective is to determine if the chelation-based strategy increases the time to composite endpoint compared with the placebo chelation strategy. The primary composite endpoint will be analyzed using a Cox proportional hazards regression model of time from randomization to the first occurrence of all-cause mortality, MI, stroke, coronary revascularization, or hospitalization for unstable angina.

The primary analysis will be based on a Cox model which includes indicator variables for the active chelation as the primary variable of interest and active OMVM groups, age, sex, and baseline insulin use as covariates. Age will be included in the model in the form of cubic splines using three knots at 10th, 50th, and 90th percentiles. Two separate manuscripts will explore the effect of active OMVM and the effects of chelation by OMVM.

The chelation treatment effect will be summarized using hazard ratios and associated 95% CIs. A hazard ratio of < 1 would suggest a benefit for the chelation-based therapy. Kaplan Meier survival estimates will be constructed based on the time from randomization to the first

primary event occurrence. Events occurring after withdrawal of consent or informed consent expiration will be censored.

The OMVM treatment effect from the Cox model will be estimated using the Cox model described above. A hazard ratio of < 1 would suggest a benefit for OMVM treatment. Given the focus on chelation therapy, the interpretation of the OMVM treatment effect will be considered exploratory. A full set of analyses of the 2x2 design will be reported in a separate manuscript.

Four interim analyses were conducted at 25%, 40%, 60%, and 80% of expected information using a Haybittle-Peto-type boundary for efficacy (i.e. $p \leq 0.001$, $Z=3$). For this reason, the adjusted two-sided significance level for the final analysis is 0.05 (i.e., the corresponding critical value, $Z = -1.96$).

Formal statistical hypothesis testing will follow a hierarchy based on statistical significance of the prior endpoint. If the prior endpoint is statistically significant at the 0.05 level, the next endpoint's p-value will be tested for significance. The outcome hierarchy will be evaluated as follows:

- 1) Primary composite outcome
- 2) Secondary all-cause mortality outcome (with conservative censoring)
- 3) Secondary composite outcome of cardiovascular mortality, MI, or stroke
- 4) Secondary recurrent event analysis (Andersen & Gill method)

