### **7.6 Safety Monitoring**

#### **Data and Safety Monitoring Board**

TACT2 will have an independent DSMB appointed by and reporting to NIH. The DSMB will be expected to meet with the study leadership at least 2 times per year to review study progress and overall safety. For ethical reasons, an interim examination of key safety and endpoint data will be performed during the course of the trial. A separate DSMB charter outlining the operating guidelines for the committee and the protocol for evaluation of data will be created prior to study enrollment and agreed upon during the initial meeting of the DSMB.

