## **9. STATISTICAL CONSIDERATIONS**

### **9.1 General Design Issues**

Analysis of the TACT2 2x2 factorial trial will be based on intention to treat (ITT). That is, participants will be analyzed (and endpoints attributed) according to the treatment strategy to which participants are randomized, regardless of subsequent additional post-randomization treatment and medical care. Statistical comparisons will be performed using two-sided significance tests. Treatment dropouts and consent withdrawals will be tracked by verifiable means within the eCRF at each follow-up interval. Baseline demographic and clinical variables will be summarized for each randomized arm of the study. Descriptive summaries of the distribution of continuous variables will be presented in terms of percentiles (e.g., median, 25th and 75th percentiles) along with means and standard deviations. Categorical variables will be summarized in terms of frequencies and percentages.

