### **9.2 Sample Size and Randomization**

Participants will be randomized in a 1:1:1:1 allocation ratio using simple randomization. The study was originally designed to enroll a total of 1200 participants with a minimum follow-up of 12 months. The DSMB conducted a blinded review of enrollment aggregate event rates, and projected event rates in July 2019. Following this blinded review, the

DSMB recommended a reduction in the target sample size to 1100 participants and an increase in the minimum follow-up from 1 year to approximately 2.5 years. Due to slowed enrollment related to the COVID-19 pandemic, in the fall of 2020, the DSMB and the NIH leadership agreed to a proposal to complete enrollment by 12/31/2020 with an allowance to follow the study participants until there are enough primary endpoint events to maintain 85+% power.

Several design factors and research objectives have been considered in developing an appropriate sample size for the TACT2 study. First, patient enrollment and follow-up has been determined so there would be a sufficient number of endpoints to provide a high degree of confidence for testing the primary hypothesis. Second, the statistical power for secondary endpoints has been considered. Finally, the sample size has been determined to provide a reasonable level of confidence for detecting clinically important differences in outcome between treatment strategies even if current projections of event rates and hypothesized differences in clinical outcomes between the treatment groups prove to be optimistic.

Table 3 shows the required number of endpoint events to have 80% to 90% power with hazard ratios varying from 0.50 to 0.75. The two factors (EDTA chelation and OMVM) are assumed to be additive for the sample size calculations. Based on TACT we anticipate a hazard ratio of 0.70 (active chelation vs. placebo chelation) to determine the sample size requirements. This hazard ratio assumption is very conservative compared to the observed effect in TACT. Assuming a two-sided 0.05 type I error rate and approximately 5% consent withdrawal or loss-to-follow-up per year, the final sample size of 1000 participants will provide approximately 85% power to detect a hazard ratio of 0.70 for the primary endpoint of time to all-cause mortality, myocardial infarction, stroke, coronary revascularization, or hospitalization for unstable angina comparing active chelation vs. placebo chelation.

Table 3. Required number of events						

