For futility monitoring, TACT2 will employ a modification of the inefficacy monitoring guideline of Freidlin, Korn, and Gray to stop the trial if the chelation strategy is not beneficial. We plan to use a conservative boundary, denoted as LIB0, along with a harm look at 25% of expected information. This approach will include 4 interim looks scheduled at roughly 25%, 40%, 60%, and 80% of expected information. With the proposed design, a total of roughly 280 primary endpoint events are expected and the first interim review for futility and efficacy will be scheduled after approximately 70 primary endpoint events have been observed. The harm look at 25% of expected information would suggest stopping the trial if the data suggests harm for the chelation strategy vs. the placebo chelation with p-values <0.05 for both the primary outcome and the all-cause mortality endpoint. For the interim reviews at 40%, 60%, and 80%, the inefficacy guideline suggests stopping the trial if the chelation infusion strategy has a hazard ratio > 1.0 compared to placebo for both the primary outcome and the all-cause mortality endpoint. This inefficacy monitoring approach will result in a trivial loss of power and requires no sample size adjustment.

The method of Haybittle and Peto will be proposed as the primary guide for interpreting interim efficacy analyses. The timing of the interim efficacy analyses will correspond to the futility monitoring reviews (i.e. at roughly 25%, 40%, 60%, and 80% of expected information). The proposed efficacy monitoring guideline requires large critical

values ( $Z=3$ ,  $p\leq 0.001$ ) for every assessment until the planned final analysis. The TACT2 investigators suggest that both the primary outcome and the all-cause mortality outcome are evaluated at the interim reviews with a focus on the comparison of active chelation vs. placebo.

The CCC PI, DCC PIs, CCC staff, clinical study Co-PIs, site investigators, NIH Program Staff and study participants will remain blinded until database lock. Limited staff will be unblinded to handle randomization codes, deliver the interventions to sites, and prepare DSMB reports. The statistical staff responsible for preparing DSMB reports will not directly interact with the clinical team that delivers care to the study participants or the CEC that determines clinical events.

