1.1 Study Design

The Trial to Assess Chelation Therapy 2 (TACT2) is a randomized, double blinded, placebo-controlled 2x2 factorial clinical trial. The study treatments are edetate disodium-based chelation (weekly infusion for 40 weeks) and high-dose oral multivitamins and multi-minerals (OMVM) (twice daily for up to 5 years). Subjects with diabetes mellitus with a prior myocardial infarction (MI) are recruited from participating sites in the US and Canada and randomized in a 1:1:1:1 fashion to 4 groups:

- i. Active chelation + active OMVM
- ii. Active chelation + placebo OMVM
- iii. Placebo chelation + active OMVM
- iv. Placebo chelation + placebo OMVM.

Patients will be followed for clinical events until the earlier of database lock or five years from randomization. Clinical outcomes will be collected by study sites at each infusion visit and by the DCRI Call Center at month 6 and 12, and every 4 months afterwards with the last assessment at month 60.

TACT2 is an event driven trial with a plan to continue until at least 282 primary endpoint events are identified. The original planned sample size was 1200 participants. The sample size was later modified to 1100. The final enrollment is 1000, but with an increased follow-up time to preserve statistical power. More details on sample size and power calculation are included later in the SAP.

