2.3 General Analysis Conventions

Statistical comparisons will be performed using two-sided significance tests. An alpha level of 0.05 will determine significance unless otherwise specified.

Continuous variables will be presented in terms of percentiles (e.g., median, 25th percentile, and 75th percentiles) along with means and standard deviations. Categorical variables will be summarized in terms of frequencies and percentages.

All programs written to create analysis datasets or perform analyses will be validated according to SOPs by the Statistical Programming group.

All statistical analysis will be performed using SAS® v9.4 or higher (Cary, NC USA) and/or other proper software, e. g. R.

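### The interim efficacy boundary is given as both Z = 3 and p ≤ 0.001, which are different thresholds, and the SAP calls an unchanged final level of 0.05 adjusted

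*SAP*

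**What the plan says.** Protocol 9.4 plans four interim reviews at roughly 25%, 40%, 60% and 80% of expected information. It proposes Haybittle-Peto as the main guide for efficacy, with a critical value of Z = 3, p ≤ 0.001, "for every assessment until the planned final analysis". It gives no level for the final analysis.

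SAP 3.2.1 reports that the four interim analyses were carried out at those fractions and repeats the same pair of thresholds. It then states: "For this reason, the adjusted two-sided significance level for the final analysis is 0.05 (i.e., the corresponding critical value", Z = −1.96).

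Both documents are explicit about sidedness and the starting alpha:
- Protocol 9.1: "Statistical comparisons will be performed using two-sided significance tests".
- Protocol 9.2, on sample size: "Assuming a two-sided 0.05 type I error rate and approximately 5% consent withdrawal or loss-to-follow-up per year".
- SAP 2.3: "An alpha level of 0.05 will determine significance unless otherwise specified".

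The unfavourable direction has its own rules in Protocol 9.4. There is a harm look at 25%. For the three later reviews, "the inefficacy guideline suggests stopping the trial if the chelation infusion strategy has a hazard ratio > 1.0 compared to placebo"; this has to hold on the primary outcome and on all-cause mortality together.

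**The concern.** The interim boundary is one decision rule and should be one number. A statistic between 3.00 and 3.29 meets the rule as a Z value and fails it as a two-sided p-value.

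The sentence on the final level says that, because of the looks, the level has been adjusted, and then gives the unadjusted value. A reader would conclude that the four looks have been allowed for and that overall alpha is 0.05. Neither document states the overall error or says that a small excess is accepted.

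The final primary test is also the gate to the formal hierarchy in SAP 3.2.1, so the level matters if the final p falls just under 0.05. The looks are already done. The operating rules were left to a document that is not among those available (Protocol 7.6: "A separate DSMB charter outlining the operating guidelines for the committee and the protocol for evaluation of data will be created"), so a reader cannot tell which boundary applied.

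**Working it through.** **Inputs.** Two-sided alpha 0.05 (Protocol 9.2, SAP 2.3). Information fractions t = 0.25, 0.40, 0.60, 0.80 and 1.00 (Protocol 9.4, SAP 3.2.1). Final critical value 1.96 (SAP 3.2.1). Hazard ratio 0.70 (Protocol 9.2). Event target 282 (SAP 1.1: "TACT2 is an event driven trial with a plan to continue until at least 282 primary endpoint events are identified"). Projected final count 288 to 299 events (SAP Table 2).

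**1. Do the two thresholds agree?** Two-sided p = 2 × [1 − Φ(Z)].
- Z = 3: p = 2 × 0.00135 = 0.0027 two-sided, 0.00135 one-sided.
- p = 0.001: |Z| = 3.29 two-sided, Z = 3.09 one-sided.

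They agree on neither reading.

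**2. The plan's event target.** Schoenfeld's formula at a hazard ratio of 0.70 and 85% power gives 283 events, and 282 events give 85.0% power. The stated 282 therefore reproduces at an unadjusted two-sided 0.05.

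**3. Overall alpha with the final test at 1.96.** Under the null the five Z statistics are jointly normal with correlation √(tᵢ/tⱼ) for tᵢ < tⱼ. With interim boundary b and symmetric crossings,

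overall alpha = 1 − P(|Z₁| < b, …, |Z₄| < b, |Z₅| < 1.96).

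This was computed by recursive numerical integration, confirmed with the multivariate normal distribution function and checked with 40 million simulated trials. The inefficacy guideline is treated as non-binding.
- b = 3: cumulative early crossing, both sides, is 0.0027, 0.0047, 0.0065 and 0.0080. The final test adds 0.0450. Total 0.0530.
- b = 3.29: early crossing reaches 0.0031. The final test adds 0.0479. Total 0.0510.

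If only early crossings in favour of chelation count, the benefit side keeps its excess and the other side is tested once at 0.025: 0.0265 + 0.025 = 0.0515 for b = 3, and 0.0255 + 0.025 = 0.0505 for b = 3.29.

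**4. Final level that holds 0.05.** Solve the same equation for the final critical value.

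| Interim boundary | Early stops counted | Overall alpha, final at 1.96 | Final Z that holds 0.05 | Final p |
|---|---|---|---|---|
| Z = 3 | both directions | 0.0530 | 1.987 | 0.0469 |
| Z = 3 | benefit only | 0.0515 | 1.973 | 0.0485 |
| two-sided p ≤ 0.001 | both directions | 0.0510 | 1.968 | 0.0490 |
| two-sided p ≤ 0.001 | benefit only | 0.0505 | 1.964 | 0.0495 |

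Reading p ≤ 0.001 as one-sided (Z = 3.09) gives 0.0521 and a final p of 0.0478 with symmetric boundaries.

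**5. Later final analysis.** If the looks were timed on 282 events and the final comes at 288 to 299, symmetric alpha is 0.0531 to 0.0533 for Z = 3, with a matching final p of 0.0468 to 0.0466. For two-sided p ≤ 0.001 it stays at 0.0510 and 0.0490.

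**6. Power cost of the matching final level** (hazard ratio 0.70, early crossings included, symmetric). Z = 3: 85.1% falls to 84.5% at 282 events, and 87.1% to 86.5% at 299. Two-sided p ≤ 0.001: 85.0% falls to 84.8% at 282 events.

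**The case against.** The strongest reply is that this is a notation slip plus one badly chosen word. Haybittle-Peto designs normally leave the final test at about 0.05 because the interim boundary is so extreme, and the SAP names a boundary of that type. The rule for the final analysis is clear, and neither document promises exact error control across looks. The convention does justify tolerating a small excess, and that part stands. It does not make Z = 3 equal to p ≤ 0.001, and it does not turn an unchanged level into an adjusted one.

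A second reply is that the largest figure, 0.053, needs Z = 3, symmetric crossing and an inefficacy guideline that is ignored. If that guideline and the harm look were followed strictly on the primary endpoint alone, the chance of a false claim of benefit, against a nominal 0.025, would be 0.0257 for Z = 3 and 0.0246 for |Z| ≥ 3.29, so in the last case there is no excess. The dependence is real and should be stated. But Protocol 9.4 words the guideline as a suggestion and requires both endpoints to point the wrong way, so this calculation overstates the reduction.

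Third, if both stated conditions had to be met, the stricter one would govern and alpha would be about 0.051 or 0.0505. That is possible, but neither document says so. Finally, the looks were only roughly at the planned fractions, so the third and fourth decimals are illustrative and any final level should be computed from the actual event counts.

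**Conclusion.** The point holds and is minor. The two interim thresholds are not equivalent on any reading, and the final level described as adjusted is the unadjusted design alpha.

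Overall two-sided alpha for the primary endpoint is about 0.0505 to 0.053, an excess of at most about 0.3 percentage points. This rests on the planned information fractions, a non-binding inefficacy guideline, and early stopping on a primary-endpoint crossing alone. Protocol 9.4 suggests looking at mortality as well but does not say whether both must cross. If both must cross, simulation with an assumed between-endpoint correlation of 0 to 0.7 puts the total at about 0.050 to 0.0505, even with Z = 3.

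The hazard ratio, its confidence interval and the model are unaffected. Significance would change only for a final p between 0.047 and 0.050 (Z = 3) or 0.049 and 0.050 (two-sided p ≤ 0.001) with symmetric boundaries. If only benefit stops count, the windows are 0.0485 to 0.050 and 0.0495 to 0.050. No error rate is claimed here for the later steps of the hierarchy.

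**What to change.** In SAP 3.2.1, consistently with Protocol 9.4, state the single efficacy boundary the DSMB used, as a Z value with its matching two-sided p. The sponsor can take this from the monitoring records. Then do one of the following:

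1. Set the final primary-endpoint level to match, computed at the actual information fractions, and use it as the entry to the hierarchy. At the planned fractions with symmetric boundaries this is about p ≤ 0.047 for Z = 3 or p ≤ 0.049 for two-sided p ≤ 0.001. It costs at most about 0.6 points of power.
2. Keep 0.05, delete the word adjusted, and report the resulting overall alpha (about 0.051 to 0.053 with symmetric boundaries) with the stopping assumption stated. This costs no power.

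Either way the change is one or two sentences. Option 2 is enough to correct the record.

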3.2.2 Sensitivity Analyses of the Primary Outcome

The primary hypothesis for the primary composite endpoint will be tested using the ITT population as a sensitivity analysis.

A sensitivity analysis was initially planned to investigate the potential effect of the COVID-19 outbreak on the primary analysis. Instead, the potential effect of COVID-19 may be explored in a separate manuscript.

A sensitivity analysis will use Bayesian methods to estimate the primary outcome treatment effect posterior distribution using the first TACT trial results and other related information to develop a set of priors for the treatment effect (Zampieri, 2020). As suggested by Zampieri, these analyses will include at least one prior distribution for the effect of chelation vs. placebo in each of the following categories: skeptical, pessimistic, and optimistic. The priors will be assumed to follow a normal distribution and will represent the log hazard ratio from the Cox model. There will be two skeptical (non-informative) priors for the log hazard ratio with a mean of zero and differing standard deviations (e.g., one standard deviation will be 10 and the other will be 100). Two pessimistic priors for the log hazard ratio will also be included, both will be centered around zero and allow for low probability of a favorable treatment effect (e.g., 0.5%

and 2.5% probability of the hazard ratio for chelation of 0.80 compared to placebo). The two optimistic priors will include the overall treatment effect from TACT (e.g., HR of 0.82 with a 95% CI of 0.69 to 0.99) and diabetes subgroup treatment effect from TACT (e.g., HR of 0.59 with a 95% CI of 0.44 to 0.79). In all of the above models, the priors for the parameters associated with other model covariates will be non-informative with large standard deviations (e.g., standard deviation of 100) and center at zero for the associated log hazard ratios. The chelation treatment effect will be summarized using mean posterior hazard ratios and associated 95% highest posterior density credible intervals. A mean posterior hazard ratio of < 1 would suggest a benefit for the chelation-based therapy.

Another sensitivity analysis is planned to assess how the primary analysis would be affected by various assumptions regarding the occurrence of primary endpoint events among those who withdrew consent or were lost to follow-up, as was performed and published in TACT. Baseline characteristics by treatment group will be assessed for the patients who did versus did not withdraw consent or were lost to follow-up. Events will be imputed by simulation only for the consent withdrawal or lost patients who did not have a documented occurrence of one of the primary events prior to the withdrawn consent/lost to follow-up. The different percentages of the withdrawn or lost patients will be assumed to have an event at their censoring time. The event rates among patients that withdrew or were lost to follow-up in each treatment group will be varied across a broad spectrum and include scenarios that were markedly unfavorable to chelation. The imputed event rates for patients who withdrew consent or were lost to follow-up will be combined with the observed event rates of patients who completed the study to assess the treatment effect via a hazard ratio. These analyses will focus on scenarios in which events among withdrawn or lost patients in the active arm are assumed to occur at a higher rate than withdrawn or lost patients in the placebo arm.

Another sensitivity analysis is planned for the primary endpoint to censor, at the point of last contact, those deaths that were identified more than one year following the most recent study contact.

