Sensitivity Analysis of the Secondary All-Cause Mortality Outcome / Bayesian analysis using TACT results as one of the priors / mITT	*Same as primary analysis	Treatment effect mean posterior hazard ratio based on a Bayesian time to event model	*Same as primary analysis	*Same as primary analysis
Sensitivity Analysis of the Primary Outcome / ITT	*Same as primary analysis	*Same as primary analysis	*Same as primary analysis	*Same as primary analysis
Sensitivity Analysis of the Primary Outcome / mITT with imputed event status for subjects withdrew /lost to follow up	*Same as primary analysis	*Same as primary analysis	*Same as primary analysis except that the event status will be imputed for subjects who withdrew consent or lost to follow up before study completion	*Same as primary analysis

Sensitivity Analysis of the Primary Outcome/ mITT with the exclusion of positively adjudicated events > 1 year after the last contact where all components of the composite were assessed
	
*Same as primary analysis
	
*Same as primary analysis
	
*Same as primary analysis but exclude positively adjudicated events more than 1 year from the most recent study contact where all components of the composite endpoint were assessed.
	
Among subjects not experiencing endpoint of interest or experiencing first CEC event > 1 year after event assessment date: Censoring date = min(date withdraw consent, date of last contact with patient/proxy where event status was assessed)
 
*Date of last contact defined in 1st row, 5th column (primary endpoint)

Sensitivity Analysis of the Secondary Composite Outcome/ Where undetermined death is considered CV-death / mITT
	
*same as secondary composite endpoint
	
*same as secondary composite endpoint, where: Undetermined death is analyzed as CV-death.
	
*same as secondary composite endpoint
	
*same as secondary composite endpoint

Sensitivity Analysis of the Secondary Composite Objective / Cause of death based on best available data (from CEC or CRF if CEC is unavailable) / mITT
	
*Same as secondary composite analysis
	
*Same as secondary composite analysis
	
*Same as secondary composite analysis, where: Cause of death is determined based on best available data. If cause of death from CEC is available, use CEC cause of death. Otherwise, if CRF cause of death available, use CRF cause of death.
	
*Same as secondary composite analysis

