3.3.3 Sensitivity Analyses of the Secondary Outcomes

A sensitivity analysis is planned for the secondary composite endpoint where undetermined death will be classified as CV-death.

Another sensitivity analysis is planned for the secondary composite endpoint where cause of death is determined based on the best available data. Cause of death will first be determined based on the data from the CEC. If cause of death from the CEC is unavailable, cause of death will be determined from the CRF data. If cause of death from the CEC and CRF is unavailable, cause of death will be determined based on the NDI data.

A sensitivity analysis is planned for the secondary all-cause mortality endpoint where participants with no event will be censored at the last date that NDI results were assessed. The censoring date will be consistent for all participants without an event.

A sensitivity analysis will use Bayesian methods to estimate the secondary all-cause mortality outcome treatment effect posterior distribution. These analyses will be performed in an analogous manner as the Bayesian analysis of the primary outcome (section 3.2.2).

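### The Bayesian sensitivity analyses include no prior centred on harm despite a category called pessimistic, and their one interpretive sentence says little under the two TACT priors

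*SAP*

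**What the plan says.** SAP 3.2.2 undertakes to use at least one prior "in each of the following categories: skeptical, pessimistic, and optimistic". On their form it says: "The priors will be assumed to follow a normal distribution and will represent the log hazard ratio from the Cox model". Six are described, with most parameters given as examples:

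- **Called skeptical:** "two skeptical (non-informative) priors for the log hazard ratio with a mean of zero", with SDs of 10 and 100.
- **Called pessimistic:** "Two pessimistic priors for the log hazard ratio will also be included, both will be centered around zero". Their spread is set by a 0.5% or a 2.5% probability attached to HR 0.80.
- **Called optimistic:** the overall TACT result, HR 0.82 (0.69 to 0.99), and the TACT diabetes result, HR 0.59 (0.44 to 0.79).

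On reporting: "The chelation treatment effect will be summarized using mean posterior hazard ratios and associated 95% highest posterior density credible intervals". The only statement on interpretation follows it: "A mean posterior hazard ratio of < 1 would suggest a benefit for the chelation-based therapy". There is no posterior probability, and nothing on how the six results are to be weighed together.

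SAP 3.3.3 extends the method to all-cause mortality, in an "analogous manner as the Bayesian analysis of the primary outcome". SAP 3.1.1, Table 3 has a row titled "Sensitivity Analysis of the Secondary All-Cause Mortality Outcome / Bayesian analysis using TACT results as one of the priors". Its endpoint, event and censoring cells all refer back to the primary analysis.

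**The concern.** A set of priors is useful in a sensitivity analysis when it spans the views that readers might hold. Here the category names suggest such a span, but the parameters do not deliver it. Two priors are flat, two are centred on no effect and two on benefit. A reader who expected harm has no prior in the set, although one category name implies that this view is covered.

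The interpretive sentence uses only which side of 1 the posterior mean falls on. Under a strong prior centred on benefit, that side is nearly settled before TACT2 reports. TACT2 is meant to replicate TACT, so supporting evidence that leans mainly on TACT should be visibly marked as such.

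The Table 3 row matters because the two endpoints follow different rules. The primary composite leaves out events after consent withdrawal or expiry of the consent form. All-cause mortality counts deaths after either. As written, the table and SAP 3.3.3 describe different analyses.

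**Working it through.** **Inputs.** TACT2 continues to at least 282 primary events (SAP 1.1). Protocol Table 3 gives the same number for 85% power at HR 0.70, and it reproduces: 4 × (1.960 + 1.036)² / (ln 0.70)² = 282.3.

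**Method.** The calculation is a normal update on the log HR that ignores covariate adjustment.

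- Data: SE = 2/√282 = 0.119, so the precision is w₁ = 282/4 = 70.5.
- Prior: mean m, SD s, precision w₀ = 1/s², worth 4/s² events.
- Posterior for an observed HR of h: variance v = 1/(w₀ + w₁), mean μ = v(w₀m + w₁ ln h), mean HR = exp(μ + v/2).
- The mean HR equals 1 when ln h = (−0.5 − w₀m)/w₁. This is the tipping point.

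**Prior SDs.** The 0.5% and 2.5% statements are read as P(HR < 0.80).

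- TACT overall: (ln 0.99 − ln 0.69)/3.92 = 0.092, m = −0.198, worth about 472 events.
- TACT diabetes: (ln 0.79 − ln 0.44)/3.92 = 0.149, m = −0.528, worth about 179 events.
- Zero-centred: 0.2231/2.576 = 0.087 and 0.2231/1.960 = 0.114, worth about 533 and 309 events.

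**Step 1: the labels.**

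- With SD 10, only 1.8% of the prior lies between HR 0.80 and 1.25, and 47% lies below 0.50. With SD 100 the figures are 0.2% and 50%. Neither prior shrinks the estimate toward no effect.
- A normal prior centred at zero gives P(HR < 1) = 50% and makes HR < 0.80 exactly as likely as HR > 1.25. That is skepticism, not pessimism.
- The optimistic labels are correct.

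**Step 2: the tipping points.**

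- TACT overall: w₀ = 117.9, so ln h = (−0.5 + 23.40)/70.5 = 0.325 and h = 1.38.
- TACT diabetes: w₀ = 44.86, so ln h = (−0.5 + 23.67)/70.5 = 0.329 and h = 1.39.
- Other four priors: m = 0, so ln h = −0.5/70.5 and h = 0.99.

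For scale, an observed HR of exp(1.96 × 0.119) = 1.26 already reaches two-sided 0.05 in the direction of harm.

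Under either TACT prior the posterior mean HR falls below 1 in 99.7% of trials if the true HR is 1.0, about 97% if it is 1.1, and 88–89% if it is 1.2. Under the other four it does so in 48% of trials at a true HR of 1.0.

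**Step 3: posterior mean HR (95% HPD interval where shown).**

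| Observed HR | TACT overall | TACT diabetes | Flat (both) | Zero-centred, SD 0.087 | Zero-centred, SD 0.114 |
|---|---|---|---|---|---|
| 1.00 | 0.886 (0.76–1.01) | 0.818 (0.67–0.97) | 1.007 | 1.002 | 1.003 |
| 1.10 | 0.918 (0.79–1.05) | 0.867 (0.71–1.03) | 1.108 | 1.036 | 1.050 |
| 1.20 | 0.948 (0.82–1.09) | 0.914 (0.75–1.08) | 1.209 | 1.068 | 1.095 |

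**Step 4: sensitivity.** The calculation was repeated for 244 to 299 events (the minimum and projected scenarios at 5% dropout in SAP Appendix I). TACT prior SDs came from the CIs or p-values or, for the diabetes prior, from the 80 and 117 events in Appendix I. The TACT tipping points stay between 1.34 and 1.52.

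**Step 5: mortality.** The SAP gives no TACT mortality HR. The protocol gives a 43% reduction with P = 0.011 in the diabetes subgroup. Read as HR 0.57, this implies a prior SD of about 0.22. No projected number of TACT2 deaths is given; assuming 80 to 200, the tipping HR runs from 1.73 down to 1.25. The documents give no overall TACT mortality HR, so that prior cannot be checked.

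**The case against.** A reader might infer that the SAP has adopted a decision rule under which a null or harmful TACT2 would be reported as beneficial. The documents do not support that.

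- The sentence is a convention about direction. SAP 3.2.1 uses almost the same words for the Cox hazard ratios, and SAP 3.3.1 for the recurrent-event models. The formal decision is a two-sided 0.05 test within a fixed hierarchy that contains no Bayesian analysis. The 48% figure under the flat and zero-centred priors only reflects that a point estimate falls below 1 about half the time when there is no effect.
- The TACT priors are openly called optimistic, and pulling toward benefit is their purpose. At an observed HR of 1.10 the other four posterior means all lie above 1, and nothing in the SAP gives the optimistic pair more prominence.
- The HPD interval is reported too. Under the overall TACT prior it includes 1 at observed HRs of 1.00 and 1.20.
- It would also go too far to say that the TACT-prior results ignore the data. As the observed HR moves from 1.00 to 1.30, the posterior mean moves from 0.886 to 0.977 under the overall prior and from 0.818 to 0.960 under the diabetes prior. Only the side of 1 is nearly fixed.
- The SAP itself adds that its skeptical priors are non-informative and states that the pessimistic ones are centred at zero. The labels therefore change no computed result.

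All of this stands and limits the point to supporting evidence. It does not supply a harm-centred prior, and the interval does not remedy every case: under the diabetes prior an exactly null TACT2 still yields an interval that excludes 1. The Table 3 row is probably a clerical cross-reference, since its title names mortality, but it still contradicts SAP 3.3.3.

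**Conclusion.** The point holds for the non-confirmatory analyses only. The SAP names three categories of prior, but by their parameters the six are non-informative, skeptical and optimistic, with none centred on harm. Under the two TACT priors the directional sentence is satisfied for any observed HR up to about 1.38–1.39 at 282 events, so it carries almost no information there. The confirmatory test, type I error and power do not change, and the other four priors would not show benefit at an observed HR of 1.0 or above. Separately, the Bayesian mortality row of Table 3 refers to the wrong endpoint, event and censoring rules.

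The figures rest on SE = 2/√events, normal priors rebuilt from the SAP's example values, and the tail-probability reading of HR 0.80. They concern the primary composite; the mortality figures depend on an assumed number of deaths.

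**What to change.** 1. In SAP 3.2.2, call the SD 10 and SD 100 priors non-informative and the two zero-centred priors skeptical.
2. Add at least one prior centred above HR 1. A mirror image of a TACT prior would serve; for the overall result that is mean +0.198 (HR 1.22) and SD 0.092. The exact location is a matter of preference.
3. Replace the directional sentence with a commitment to report P(HR < 1) and the 95% credible interval under every prior, and state that results under the optimistic priors are read only beside the others. The second half is needed: at an observed HR of 1.00 the diabetes prior alone gives P(HR < 1) of about 0.99 (μ = −23.67/115.36 = −0.205, posterior SD 0.093), against 0.50 under each of the other four non-TACT priors. A further cut-off such as P(HR < 0.90), or a fixed probability threshold, is optional.
4. In SAP Table 3, refer the Bayesian mortality row to the secondary all-cause mortality analysis, and in SAP 3.3.3 state the TACT mortality results from which its TACT priors are built.

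The cost is SAP wording and one or two more model runs. The Bayesian summary becomes less easily favourable to chelation.
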